Appendix 13: Study Details Specific to Atezo + Tira Arm

- Myelitis
- Facial paresis

A13–5.3 REPORTING REQUIREMENTS FOR PREGNANCIES IN THE ATEZO+TIRA ARM

A13–5.3.1 Pregnancies in Female Patients

Female patients of childbearing potential will be instructed through the Informed Consent Form to immediately inform the investigator if they become pregnant during the study or within 5 months after the final dose of atezolizumab or within 90 days after the final dose of tiragolumab. A paper Clinical Trial Pregnancy Reporting Form should be completed and submitted to the Sponsor or its designee immediately (i.e., no more than 24 hours after learning of the pregnancy), either by faxing or by scanning and e-mailing the form using the fax number or e-mail address provided to investigators. Pregnancy should not be recorded on the Adverse Event eCRF. The investigator should discontinue study treatment and counsel the patient, discussing the risks of the pregnancy and the possible effects on the fetus. Monitoring of the patient should continue until conclusion of the pregnancy. Any serious adverse events associated with the pregnancy (e.g., an event in the fetus, an event in the mother during or after the pregnancy, or a congenital anomaly/birth defect in the child) should be reported on the Adverse Event eCRF. In addition, the investigator will submit a Clinical Trial Pregnancy Reporting Form when updated information on the course and outcome of the pregnancy becomes available.

Attempts should be made to collect and report infant health information. When permitted by the site, an Authorization for the Use and Disclosure of Infant Health Information would need to be signed by one or both parents (as per local regulations) to allow for follow-up on the infant. If the authorization has been signed, the infant's health status at birth should be recorded on the Clinical Trial Pregnancy Reporting Form. In addition, the Sponsor may collect follow-up information on the infant's health status at 6 and 12 months after birth.

A13–5.3.2 Pregnancies in Female Partners of Male Patients

Male patients will be instructed through the Informed Consent Form to immediately inform the investigator if their partner becomes pregnant during the study or within 90 days after the final dose of tiragolumab. The investigator should report the pregnancy on the paper Clinical Trial Pregnancy Reporting Form and submit the form to the Sponsor or its designee immediately (i.e., no more than 24 hours after learning of the pregnancy), either by faxing or by scanning and e-mailing the form using the fax number or e-mail address provided to investigators. Attempts should be made to collect and report details of the course and outcome of any pregnancy in the partner of a male patient exposed to study treatment. When permitted by the site, the pregnant partner would need to sign an Authorization for the Use and Disclosure of Pregnancy Health

Appendix 13: Study Details Specific to Atezo + Tira Arm

Information to allow for follow-up on her pregnancy. If the authorization has been signed, the investigator should submit a Clinical Trial Pregnancy Reporting Form with additional information on the pregnant partner and the course and outcome of the pregnancy as it becomes available.

Attempts should be made to collect and report infant health information. When permitted by the site, an Authorization for the Use and Disclosure of Infant Health Information would need to be signed by one or both parents (as per local regulations) to allow for follow-up on the infant. If the authorization has been signed, the infant's health status at birth should be recorded on the Clinical Trial Pregnancy Reporting Form. In addition, the Sponsor may collect follow-up information on the infant's health status at 6 and 12 months after birth.

An investigator who is contacted by the male patient or his pregnant partner may provide information on the risks of the pregnancy and the possible effects on the fetus, to support an informed decision in cooperation with the treating physician and/or obstetrician.

A13–5.3.3 Abortions

A spontaneous abortion should be classified as a serious adverse event (as the Sponsor considers abortions to be medically significant), recorded on the Adverse Event eCRF, and reported to the Sponsor immediately (i.e., no more than 24 hours after learning of the event; see Section [5.4.2](#)).

If a therapeutic or elective abortion was performed because of an underlying maternal or embryofetal toxicity, the toxicity should be classified as a serious adverse event, recorded on the Adverse Event eCRF, and reported to the Sponsor immediately (i.e., no more than 24 hours after learning of the event; see Section [5.4.2](#)). A therapeutic or elective abortion performed for reasons other than an underlying maternal or embryofetal toxicity is not considered an adverse event.

All abortions should be reported as pregnancy outcomes on the paper Clinical Trial Pregnancy Reporting Form.

A13–5.3.4 Congenital Anomalies/Birth Defects

Any congenital anomaly/birth defect in a child born to a female patient exposed to study treatment or the female partner of a male patient exposed to study treatment should be classified as a serious adverse event, recorded on the Adverse Event eCRF, and reported to the Sponsor immediately (i.e., no more than 24 hours after learning of the event; see Section [5.2.2](#)).

Appendix 13: Study Details Specific to Atezo + Tira Arm

A13-6 SCHEDULES OF ACTIVITIES AND SAMPLE COLLECTION FOR ATEZO + TIRA ARM

Table A13-6 Schedule of Activities for Atezo+Tira Arm

Assessment/ Procedure ^a	Protocol Section	Screening (see Appendix 10)	Treatment Cycles (21-Day Cycles)		Pre-Surgery	Surgery CLND	Post-Surgery	Treatment Comp./ Discon. ^b	Long- Term Follow- Up	Surgery Follow-Up ^c	
			Cycle 1	Cycle 2							
		D –28 to D –1	D1 (≤7D after randomization)	D1 (+ 1D)	Wk 6 (≤8D to surgery)	Wk 7 (± 7D)	Wk 10 (≥20D after surgery)	Wk 13	Every 3M (±7D)	6M after surgery (±7D)	
IMP Administration											
Atezolizumab administration	A13-4.1.2			x	x						
Tiragolumab administration				x	x						
Clinical Assessments											
Molecular profile of melanoma	4.5.2		Whenever updated information becomes available								
Weight ^d	4.5.3		x	x	x		x	x		x	
Complete physical examination									x		
Limited physical examination ^d			x	x	x		x			x	
Vital signs	4.5.4 and A13-4.1.2		x	x	x		x	x		x	
12-Lead ECG ^d	4.5.5		x	x				x			
TTE or MUGA scan	4.5.6							x			

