Appendix 12: Study Details Specific to RO7247669 2100 mg Arm

A12–5.2 ADVERSE EVENTS OF SPECIAL INTEREST FOR RO7247669 2100 mg ARM (IMMEDIATELY REPORTABLE TO THE SPONSOR)

Adverse events of special interest are required to be reported by the investigator to the Sponsor immediately (i.e., no more than 24 hours after learning of the event; see Section 5.2.3 for reporting instructions). Adverse events of special interest for the RO7247669 2100 mg arm are as follows:

- Cases of potential drug-induced liver injury that include an elevated ALT or AST in combination with either elevated bilirubin or clinical jaundice, as defined by Hy's Law (see Section 5.3.5.7)
- Suspected transmission of an infectious agent by the study treatment, as defined below:

Any organism, virus, or infectious particle (e.g., prion protein transmitting transmissible spongiform encephalopathy), pathogenic or non-pathogenic, is considered an infectious agent. A transmission of an infectious agent may be suspected from clinical symptoms or laboratory findings that indicate an infection in a patient exposed to a medicinal product. This term applies only when a contamination of study treatment is suspected.

A12–5.3 REPORTING REQUIREMENTS FOR PREGNANCIES IN RO7247669 2100 mg ARM

A12–5.3.1 Pregnancies in Female Patients

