Appendix 13: Study Details Specific to Atezo + Tira Arm

A13–5.2 ADVERSE EVENTS OF SPECIAL INTEREST FOR THE ATEZO + TIRA ARM (IMMEDIATELY REPORTABLE TO THE SPONSOR)

Adverse events of special interest are required to be reported by the investigator to the Sponsor immediately (i.e., no more than 24 hours after learning of the event; see Section 5.2.3 for reporting instructions). Adverse events of special interest for the Atezo + Tira arm are as follows:

- Cases of potential drug-induced liver injury that include an elevated ALT or AST in combination with either elevated bilirubin or clinical jaundice, as defined by Hy's Law (see Section 5.3.5.7)
- Suspected transmission of an infectious agent by the study treatment, as defined below:

Any organism, virus, or infectious particle (e.g., prion protein transmitting transmissible spongiform encephalopathy), pathogenic or non-pathogenic, is considered an infectious agent. A transmission of an infectious agent may be suspected from clinical symptoms or laboratory findings that indicate an infection in a patient exposed to a medicinal product. This term applies only when a contamination of study treatment is suspected.

- Pneumonitis
- Colitis
- Endocrinopathies: diabetes mellitus, pancreatitis, adrenal insufficiency, hyperthyroidism, and hypophysitis
- Hepatitis, including AST or ALT $> 10 \times$ upper limit of normal
- Systemic lupus erythematosus
- Neurological disorders: Guillain-Barré syndrome, myasthenic syndrome or myasthenia gravis, and meningoencephalitis
- Events suggestive of hypersensitivity, IRRs, cytokine-release syndrome, influenza-like illness, HLH, and MAS
- Nephritis
- Ocular toxicities (e.g., uveitis, retinitis, and optic neuritis)
- Myositis
- Myopathies, including rhabdomyolysis
- Grade ≥ 2 cardiac disorders (e.g., atrial fibrillation, myocarditis, pericarditis)
- Vasculitis
- Autoimmune hemolytic anemia
- Severe cutaneous reactions (e.g., Stevens-Johnson syndrome, dermatitis bullous, toxic epidermal necrolysis)

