Appendix 15: Study Details Specific to RO7247669 600 mg Arm

A15-5.2 ADVERSE EVENTS OF SPECIAL INTEREST FOR RO7247669 600 mg ARM (IMMEDIATELY REPORTABLE TO THE SPONSOR)

Adverse events of special interest are required to be reported by the investigator to the Sponsor immediately (i.e., no more than 24 hours after learning of the event; see Section 5.2.3 for reporting instructions). Adverse events of special interest for the RO7247669 600 mg arm are as follows:

- Cases of potential drug-induced liver injury that include an elevated ALT or AST in combination with either elevated bilirubin or clinical jaundice, as defined by Hy's Law (see Section 5.3.5.7)
- Suspected transmission of an infectious agent by the study treatment, as defined below:

Any organism, virus, or infectious particle (e.g., prion protein transmitting transmissible spongiform encephalopathy), pathogenic or non-pathogenic, is considered an infectious agent. A transmission of an infectious agent may be suspected from clinical symptoms or laboratory findings that indicate an infection in a patient exposed to a medicinal product. This term applies only when a contamination of study treatment is suspected.

A15-5.3 REPORTING REQUIREMENTS FOR PREGNANCIES IN RO7247669 600 mg ARM

A15-5.3.1 Pregnancies in Female Patients

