Appendix 16: Study Details Specific to RO7247669 600 mg + Tira Arm

A16-6 SCHEDULES OF ACTIVITIES AND SAMPLE COLLECTION FOR RO7247669 600 mg+TIRA ARM

Table A16-5 Schedule of Activities for RO7247669 600 mg+Tira Arm

Assessment/ Procedure ^a	Protocol Section	Screening (see Appendix 10)	Treatment Cycles (21-Day Cycles)		Pre-Surgery	Surgery CLND	Post-Surgery	Treatment Comp./ Discon. ^b	Long- Term Follow- Up	Surgery Follow-Up ^c	
			Cycle 1	Cycle 2							
			D-28 to D-1	D1 (≤7D after randomization)	D1 (+1D)	Wk 6 (≤8D to surgery)	Wk 7 (±7D)	Wk 10 (≥20D after surgery)	Wk 13		
IMP Administration											
RO7247669 600 mg administration	A16-4.1.2			x	x						
Tiragolumab administration				x	x						
Clinical Assessments											
Molecular profile of melanoma	4.5.2		Whenever updated information becomes available								
Weight ^d	4.5.3		x	x	x		x	x		x	
Complete physical examination								x			
Limited physical examination ^d			x	x	x		x			x	
Vital signs	4.5.4 and A16-4.1.2		x	x	x		x	x		x	
12-Lead ECG ^d	4.5.5		x	x			x	x			
TTE or MUGA scan	4.5.6							x			

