Appendix 16: Study Details Specific to RO7247669 600 mg+Tira Arm

Table A16-5 SCHEDULE OF ACTIVITIES FOR RO7247669 600 mg+TIRA ARM (cont.)

Assessment/ Procedure ^a	Protocol Section	Screening (see Appendix 10)	Treatment Cycles (21-Day Cycles)		Pre-Surgery	Surgery CLND	Post-Surgery	Treatment Comp./ Discon. ^b	Long- Term Follow- Up	Surgery Follow-Up ^c
			Cycle 1	Cycle 2						
		D-28 to D-1	D1 (≤7D after randomization)	D1 (+1D)	Wk 6 (≤8D to surgery)	Wk 7 (±7D)	Wk 10 (≥20D after surgery)	Wk 13	Every 3M (±7D)	6M after surgery (±7D)
Central Laboratory Assessments (cont.)										
Blood and plasma samples for biomarkers	4.5.9.2		Refer to Section A16-7.						X (only if onsite)	Refer to Section A16-7.
Pre-dose tumor biopsy				x ^d						
Resected tissue						x				
Tumor biopsy (optional)			Perform at the time of unacceptable toxicity, loss of clinical benefit, relapse, or at any other time if deemed clinically feasible by the investigator.							

ADA=anti-drug antibody; CLND=complete lymph node dissection; Comp.=completion; CT=computed tomography; D=day; Discon.=discontinuation; ECOG=Eastern Cooperative Oncology Group; IMP=investigational medicinal product; M=month; MUGA=multiple-gated acquisition; PK=pharmacokinetic; T3=triiodothyronine; T4=thyroxine; TSH=thyroid-stimulating hormone; TTE=transthoracic echocardiogram; Wk=week.

Note: On treatment days, all assessments and procedures should be performed prior to dosing, unless otherwise specified.

- ^a If a visit is precluded because of a holiday, vacation, or other circumstance, it can occur outside of the specified window.
- ^b Regardless of whether they complete the study drug treatment period or discontinue study drug prematurely, patients who proceed to surgery will return to the clinic for a treatment completion/discontinuation visit 6 weeks after surgery and patients who do not proceed to surgery will return to the clinic for a treatment completion/discontinuation visit not more than 30 days after the final dose of study treatment.
- ^c Patients who proceed to surgery will have the surgery follow-up 6 months after surgery.
- ^d Assessment may be performed within 24 hours prior to dosing during the treatment period.
- ^e The disease status assessments at Week 13 should include a mandatory CT scan.

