^g Patients who complete the treatment period, regardless of whether they complete the study drug treatment period or discontinue study drug prematurely, patients who proceed to surgery will have their first long-term follow-up visit 3 months after surgery and patients who do not proceed to surgery will have their first long-term follow-up visit 3 months after the final dose of study treatment. Information on survival follow-up and new anti-cancer therapy (including targeted therapy and immunotherapy) will be collected via telephone calls, patient medical records, and/or clinic visits approximately every 3 months until death (unless the patient withdraws consent or the Sponsor terminates the study). If a patient requests to be withdrawn from follow-up, this request must be documented in the source documents and signed by the investigator. If a patient withdraws from the study, the study staff may use a public information source (e.g., county records) to obtain information about survival status only. For an experimental arm in which all patients discontinued treatment and passed the safety follow-up window, as well as approximately 80% of patients discontinued the study, the Sponsor may conclude the arm (the remaining ~20% of patients will be discontinued from the study).

^h Laboratory tests must be performed within 72 hours prior to dosing during the treatment period. If screening laboratory assessments were performed within 72 hours prior to Day 1 of Cycle 1, they do not have to be repeated.

ⁱ At the pre-surgery visit, adrenocorticotropic hormone, cortisol, S100, and erythrocyte sedimentation rate will be included in the chemistry panel.

^j This is only applicable if elevated levels of cardiac enzymes were detected in previous assessments.

^k If periods are missed or delayed before the 6-month follow-up visit, pregnancy testing should be repeated. This test can be performed by a local gynecologist.

^l The Cycle 2 Day 1 on-treatment tissue sample must be collected up to 72 hours prior to drug administration.

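### Table A16-5 gives the RO7247669 600 mg + Tira arm a Week 10 ECG that no other Cohort 1 schedule has, so ECG-detected cardiac events can be ascertained unequally

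*Combined protocol and SAP*

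**What the plan says.** Six schedules of activities cover Cohort 1: Tables A11-2 (Nivo + Ipi control), A12-4 (RO7247669 2100 mg), A13-6 (Atezo + Tira), A14-5 (RO7247669 2100 mg + Tira, Cohort 1), A15-4 (RO7247669 600 mg) and A16-5 (RO7247669 600 mg + Tira).

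In Table A13-6 the row is "12-Lead ECG ^d 4.5.5 x x x", and the marks fall under Cycle 1 Day 1, Cycle 2 Day 1 and Week 13. Tables A11-2, A12-4, A14-5 and A15-4 mark the same three visits. In Table A16-5 the row is "12-Lead ECG ^d 4.5.5 x x x x", and the additional mark falls under the post-surgery Week 10 visit.

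Footnote d is attached to the ECG row in all six tables and concerns timing relative to dosing only: "Assessment may be performed within 24 hours prior to dosing during the treatment period". A general note to each table puts treatment-day assessments before the infusion.

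The other scheduled cardiac tests do not differ between arms. The row "TTE or MUGA scan" is marked at Week 13. Cardiac enzymes are measured at both treatment visits and Week 13, and the pre-surgery measurement is conditional: "This is only applicable if elevated levels of cardiac enzymes were detected in previous assessments".

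The special-interest lists of the three tiragolumab doublets (Sections A13-5.2, A14-5.2 and A16-5.2) include Grade 2 or higher "cardiac disorders (e.g., atrial fibrillation, myocarditis, pericarditis". In all three, adverse events of special interest are reported for 135 days after the final dose, or until new systemic anti-cancer therapy if that comes first. Other non-serious events are generally reported for 30 days.

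**The concern.** An extra scheduled test is an extra chance to find an event that produces no symptoms. If one arm has an ECG at a visit where the others have none, a transient rhythm abnormality around that time can be recorded in that arm and missed elsewhere. The recorded rates could then differ even if the true rates were equal.

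The comparison most exposed is among the tiragolumab doublets, because the item definition and the reporting window are common to them. Within that group, the 2100 mg + Tira and 600 mg + Tira arms differ in the RO7247669 dose. Section A16-3.1 argues that more than 600 mg is not expected to add clinical activity, so how the two doses compare on safety is of real interest. Any excess from the schedule would count against the 600 mg combination.

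**Working it through.** The documents give no figure to reproduce here. The check is a reading of the tables, followed by an illustration of size.

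**1. ECG marks by arm**

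| Schedule | C1D1 | C2D1 | Week 10 | Week 13 | Total | After dose 2 |
|---|---|---|---|---|---|---|
| A11-2 Nivo + Ipi | x | x | | x | 3 | 1 |
| A12-4 RO7247669 2100 mg | x | x | | x | 3 | 1 |
| A13-6 Atezo + Tira | x | x | | x | 3 | 1 |
| A14-5 RO7247669 2100 mg + Tira | x | x | | x | 3 | 1 |
| A15-4 RO7247669 600 mg | x | x | | x | 3 | 1 |
| A16-5 RO7247669 600 mg + Tira | x | x | x | x | 4 | 2 |

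The Cycle 2 Day 1 ECG precedes the infusion, so it is not counted as after dose 2.

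**2. Is it a shifted column?** In Table A16-5 the weight and vital-sign rows carry Week 10 and Week 13 marks in the same positions as in Table A13-6, and the echocardiography/MUGA row falls on Week 13 in both. Among these rows only the ECG row differs, so a shift is unlikely.

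**3. All scheduled cardiac tests after dose 2.** Counting ECG, echocardiography/MUGA and unconditional enzymes: 2 + 1 + 1 = 4 in the 600 mg + Tira arm, against 1 + 1 + 1 = 3 elsewhere, a ratio of 4/3 = 1.33.

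**4. Which reporting window applies?** Dose 2 is on Day 22 and surgery is in Week 7 (Days 43 to 49). The Week 10 visit is at least 20 days after surgery:

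- 43 + 20 − 22 = 41 days after dose 2
- 49 + 20 − 22 = 47 days after dose 2

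The 7-day surgery tolerance brings the earliest case to 36 + 20 − 22 = 34 days. All of these are past the 30-day window for other events. The later ECG, 6 weeks after surgery, falls at 43 + 42 − 22 = 63 to 49 + 42 − 22 = 69 days. Both visits lie inside the 135-day window. The two ECGs are at most 42 − 20 = 22 days apart if the visits are on schedule.

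**5. Illustrative size.** Neither a detection rate nor the arm size is taken from the documents. Assume 20 patients in the arm, all having surgery. Assume also that each ECG finds an otherwise unrecognised qualifying event with probability p, independently of the other ECG. Two ECGs then find at least one with probability 1 − (1 − p)².

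| p | One ECG | Two ECGs | Extra events in 20 patients |
|---|---|---|---|
| 1% | 1.0% | 1.99% | 20 × 0.0099 = 0.2 |
| 2% | 2.0% | 3.96% | 20 × 0.0196 = 0.4 |
| 5% | 5.0% | 9.75% | 20 × 0.0475 = 0.95 |

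Independence gives a larger excess than positively correlated findings would. If every abnormality present at Week 10 persists to Week 13, the second look adds no patients, only an earlier date of detection. The range therefore starts at zero.

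**The case against.** The strongest case against is that the point rests on a single mark in tables that do not all convert cleanly to text. The ECOG rows of Tables A13-6 and A15-4, for example, are visibly disturbed. Matching neighbouring rows cannot prove that a different row is intact. This stands as a caution: a stray mark cannot be fully excluded, and the cell should be confirmed on the original page.

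Section 4.5.5, to which every ECG row refers, and the statistical sections were not in the part of the document reviewed. A common rule in Section 4.5.5 would not make the six tables agree, but it could show which is intended. No text reviewed plans a between-arm test of cardiac events or a formal safety comparison of the two doses. The harm is therefore to the reading of descriptive tables, not to a stated test.

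A reader might infer that cardiac events of special interest are looked for twice as often in this arm as in every other Cohort 1 arm, and that the arm will show more of them, and earlier. The documents do not support that, for four reasons:

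- The 2-to-1 ratio holds only for scheduled ECGs after dose 2. From Cycle 1 Day 1 it is 4 to 3, the other cardiac tests are equal, and symptomatic events are reported however they are found.
- The item is not common to all arms. The list in Section A12-5.2 that opens "Adverse events of special interest for the RO7247669 2100 mg arm are as follows" contains only potential drug-induced liver injury and suspected transmission of an infectious agent, and Section A15-5.2 is the same. The control arm's list was not available. Against the single-agent arms, such a comparison is already unequal by definition.
- The Week 10 visit is post-surgery. Patients without surgery instead return within 30 days of their last dose, and the extra ECG does not reach them.
- Whether more events would appear depends on how long abnormalities last and how often they go unnoticed. The documents give neither.

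**Conclusion.** The inconsistency holds: one of six parallel schedules carries a Week 10 ECG without explanation. Added caution is not given as a reason. Section A16-5.1 leaves out the safety run-in and safety evaluation phase that Section A14-5.1 describes for the 2100 mg doublet.

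The supported conclusion is that ECG-detected cardiac events can be ascertained unequally for patients who have surgery, chiefly between the 600 mg + Tira arm and the Atezo + Tira and 2100 mg + Tira arms. The likely size is zero to about one event in the arm, on the assumed 20 patients, detection probabilities of 1% to 5% per ECG, and findings ranging from fully persistent to independent. The excess shrinks in proportion if fewer patients have surgery. This is a minor point, but it concerns an operational schedule that sites will follow.

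**What to change.** Confirm the Week 10 cell in Table A16-5, then reconcile its 12-lead ECG row with Section 4.5.5 and the other five Cohort 1 schedules so that the same visits carry an ECG in every arm. The sponsor decides which visits. If the difference is intended, the reason should be stated.

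For data already collected under unequal schedules, keep all cardiac events in the main safety tables. Flag those in the 600 mg + Tira arm first found at a Week 10 ECG, and add one sensitivity summary without them. Dropping Week 10 findings from the main table would remove real safety information and is not advised.

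The cost is one table correction at the next amendment and one extra flag. The text reviewed does not show that the adverse event form records how an event was found, so the flag may have to be derived from event and ECG dates, with a site query where these are ambiguous.
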